5.2 Inclusion of Women and Minorities

The study is open to anyone regardless of gender or ethnicity. Efforts will be made to extend the accrual to a representative population, but in a trial which will accrue approximately 52 subjects, a balance must be struck between subject safety considerations and limitations on the number of individuals exposed to potentially toxic or ineffective treatments on the one hand and the need to explore gender, racial, and ethnic aspects of clinical research on the other. If differences in outcome that correlate to gender, racial, or ethnic identity are noted, accrual may be expanded or additional studies may be performed to investigate those differences more fully.

6.0 PARTICIPANT ENROLLMENT

6.1 Pre-Enrollment Informed Consent and Screening Procedures

Diagnostic or laboratory studies performed exclusively to determine eligibility will be done only after obtaining written informed consent. As long as they were performed within the appropriate time frame, studies or procedures that are performed for clinical indications (not exclusively to determine study eligibility) may be used for baseline values and/or to determine pre-eligibility, even if the studies were done before informed consent was obtained. Reference is made to Section 8.0 - Study Calendar. The informed consent process is to be fully documented, and the prospective participant must receive a copy of the signed informed consent document.

6.2 Participant Enrollment

6.2.1 COH DCC Availability and Contact Information

Eligible participants will be registered on the study centrally by the DCC at City of Hope. DCC staff are available **between the hours of 8:00 a.m. and 5:00 p.m. PST, Monday through Friday (except holidays)**. DCC contact information is as follows:

- e-mail: [contact]

6.2.2 Slot verification and reservation

During the dose escalation stage, eligible Phase 1 participants will be assigned a dose level (Section 7.0). Once the recommended phase 2 dose (RP2D) is defined, participants will enroll at the RP2D dose (expansion cohort).

Issues that would cause treatment delays should be discussed with the Principal Investigator.

Designated study staff should call the DCC to verify current slot availability, and to reserve a slot for a specific prospective subject.

The DCC should be notified of cancellations of prospective participants holding slots as soon as possible.

6.3 Screen Failures and Registered Participants Who Do Not begin Study Treatment

The DCC is to be notified of all participants who sign consent but do not meet eligibility criteria or do not initiate protocol therapy.

6.4 Registration Process

To register a participant, the subsequent procedure is to be followed.

1. The participating site's data manager/coordinator/research nurse should contact the DCC via telephone or email to provide notification regarding the pending registration and communicate desired timeline of the registration, especially if it must be completed promptly to meet the registration window.

2. The data manager/coordinator/research nurse should then e-mail copies to [contact] of the following documents to the DCC:
 - Completed Eligibility Criteria List (printed from Section 5.1 of the protocol)
 - Source documentation to support eligibility criteria**
 - Signed informed consent document
 - Signed HIPAA authorization form (if separate from the informed consent document)
 - Signed subject's Bill of Rights
3. After having received all transferred documentation, the DCC will complete the review the documents to verify eligibility, working with the study team as needed to resolve any missing required source elements. A participant failing to meet all protocol eligibility requirements will not be registered.
4. Once eligibility has been confirmed, DCC staff will send a Confirmation of Registration Form and signed eligibility checklist, including the participant study number to:
 - the COH Study PI and COH study team designees (including but not limited to study monitor(s) and statistician(s)).
5. Upon receipt of the Confirmation of Registration Form, COH study team will register the patient in OnCore.

7.0 TREATMENT PROGRAM

The agents to be used in this trial are outlined below in Table 2:

Table 2. Study Agents

Study Agents					
Drug	Dose/Potency	Dose Frequency	Route of Administration	Regimen/Treatment Period	Use
Pembrolizumab	200 mg	Q3W	IV infusion	Day 1 of each 21-day cycle	Experimental
Vorinostat	100mg capsules, dose will vary by dose level	BID	Oral	Per Dose Escalation rules	Experimental

7.1 Treatment Allocation

There will be no randomization or stratification as part of this study. All patients who consent to the study, meet eligibility criteria, and are registered on the trial will receive study treatment.

This is a phase I study, including a dose-escalation portion of the study with 2 dose levels and 2 possible de-escalation dose levels, for a total of 4 possible dose levels. The starting dose will

be 100mg of vorinostat twice a day (BID), and 200mg IV pembrolizumab. Subjects will receive oral vorinostat according to dose level schedule and dose. Pembrolizumab will be administered on day 1 of each cycle thereafter. Study therapy will be administered in 21-day cycles. The planned dose levels in the dose-escalation portion of the study are outlined in Table 3 below.

Once the RP2D has been determined, an expansion cohort of 40 patients will be enrolled and treated at the RP2D, to acquire additional safety and tolerability data about the combination.

Table 3. Phase I Dose Levels

Dose Level	Vorinostat	Pembrolizumab (day 1)
-2	100mg PO BID, d1-3, 8-10	200mg IV
-1	100mg PO BID, d1-3, 8-10, 15-17	200mg IV
1 (starting)	100mg PO BID, d1-5, 8-12	200mg IV
2	200mg PO BID, d1-5, 8-12	200mg IV

7.1.1 Treatment Duration

Study treatment will continue until the subject completes 24 months of treatment with the study regimen, or experiences radiographically-confirmed PD (Section 9.2.6 and Section 9.2.6.1), unacceptable adverse experiences, either DLT (Section 7.2) or other unacceptable toxicity (section 10.2), or meets other criteria for study withdrawal or treatment discontinuation

7.1.2 Rules for Phase I Dose Escalation, De-Escalation and Expansion: Adapted Rolling 6 Design

This phase I trial will employ a modified Rolling 6 design, a more conservative version of the Rolling 6 design of Skolnik, et al²⁹. In this design, at most, 3 patients will be under observation for DLT on the current test dose level at any time. Patients who are not evaluable for DLT will be replaced. Once each patient is evaluable for toxicity and passes without a DLT, an additional patient *may* be accrued on that dose level – up to 6 patients. Once 3 patients are evaluable with no patient at that dose level experiencing a DLT, the dose can be escalated, or up to 3 additional patients may be treated at the current dose level. Although this design does not require that 6 patients be treated, no more than 6 evaluable patients will be accrued to any dose level during the dose finding portion of this study. If at any time, the dose level has 1 documented DLT with fewer than 6 evaluable patients, accrual will continue until 6 patients are evaluable. Escalation will terminate as soon as two or more patients experience any DLT attributable to the study treatment, at a given dose level. MTD will be declared at the highest dose level at which 6 patients have been treated and at most 1/6 patients experiences DLT. If more than 1/6 patients experiences DLT, then the next lower dose will be expanded. There will be no intrapatient dose escalation. These rules are outlined in Table 4:

Table 4. Dose Escalation Rules

# Patients on Current Level			Action
With DLT [^]	Evaluable	Evaluable + At Risk [^]	
0	0	1-2	Accrue next patient at this level*
0	0	3	Hold accrual
0	1	1-3	Accrue next patient at this level
0	1	4	Hold accrual
0	2	2-4	Accrue next patient at this level
0	2	5	Hold accrual
0	3-6	3-6	Accrue next patient at the next higher level* ^{+,+}
1	1	1-2	Accrue next patient at this level
1	1	3	Hold Accrual
1	2	2	Accrue next patient at this level
1	2	3-4	Hold accrual
1	3-5	3-5	Accrue next patient at this level
1	3-5	6	Hold accrual
1	6	6	Accrue next patient at the next higher level*
2**	any	any	Accrue next patient at next lower level (max 6)

[^]: DLT: a patient with a documented DLT
 Evaluable: a patient who is either fully evaluable for toxicity for the purpose of dose escalations or has a DLT
 At Risk: a patient who is on treatment and has not yet passed the evaluation period nor had a DLT
^{*}: During the dose-escalation portion, if higher dose level is already closed, the next lower dose will accrue to a total of 6 patients, with 2 or higher DLTs requiring further dose de-escalation.
⁺: Although under this scenario escalating to the next higher dose level is suggested, additional patients can be accrued to the current level -up to n=6 patients.
^{**}: Patients treated on a higher dose will have their treatment modified to the dose below the dose level with 2 DLTs, if pending patients have DLT.

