7.6.1.2 Pembrolizumab Dose Modification (Escalation/Titration/Other)

Note: If pembrolizumab administration is held for toxicity, and the toxicity is most likely attributed to pembrolizumab and not attributed to vorinostat, administration of vorinostat can continue.

During the Phase I portion of the study, no intrapatient dose de-escalation will be allowed during the DLT period. After the DLT period, the following dose modifications are permitted for pembrolizumab-related adverse events according the guidelines outlined below in Table 5 for pembrolizumab. If, according to Table 5, pembrolizumab is discontinued permanently, the patient should continue to receive vorinostat.

Adverse events (both non-serious and serious) associated with pembrolizumab exposure may represent an immunologic etiology. These immune-related adverse events may occur shortly after the first dose or several months after the last dose of pembrolizumab treatment and may affect more than one body system simultaneously. Therefore, early recognition and initiation of treatment is critical to reduce complications. Based on existing clinical study data, most irAEs were reversible and could be managed with interruptions of pembrolizumab, administration of corticosteroids and/or other supportive care. For suspected irAEs, ensure adequate evaluation to confirm etiology or exclude other causes. Additional procedures or tests such as bronchoscopy, endoscopy, skin biopsy may be included as part of the evaluation. Based on the severity of irAEs, withhold or permanently discontinue pembrolizumab and administer corticosteroids. Dose modification and toxicity management guidelines for irAEs associated with pembrolizumab are provided in Table 5. See Section 7.10.1 for supportive care guidelines, including use of corticosteroids.

Table 5. Dose modification and toxicity management guidelines for immune-related AEs associated with pembrolizumab

General instructions:

1. Corticosteroid taper should be initiated upon AE improving to Grade 1 or less and continue to taper over at least 4 weeks.
2. For situations where pembrolizumab has been withheld, pembrolizumab can be resumed after AE has been reduced to Grade 1 or 0 and corticosteroid has been tapered. Pembrolizumab should be permanently discontinued if AE does not resolve within 12 weeks of last dose or corticosteroids cannot be reduced to ≤ 10 mg prednisone or equivalent per day within 12 weeks.

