7.7.1 Vorinostat Dose/Delay Modification Guidelines

Note: If vorinostat is dose-reduced or held for toxicity, and the toxicity is most likely attributed to vorinostat and not attributed to pembrolizumab, administration of pembrolizumab can continue.

Vorinostat dose reductions are NOT permitted during the DLT period. Following the completion of the DLT period, the vorinostat doses may be modified for toxicity according to the below guidelines in Tables 6 and 7. Vorinostat dose delays are permitted during the DLT period due to study treatment-related toxicity, however, if a patient misses > 30% of the vorinostat doses due to toxicity, this will be considered a DLT.

Table 6. Vorinostat Dose Reduction Guidelines

Vorinostat Dose Reductions				
Starting dose	1 st dose reduction	2 nd dose reduction	3 rd dose reduction	4 th dose reduction
Dose Level 1	Dose Level -1	Dose Level -2	Dose Level -2 schedule but 100mg daily	N/A**
Dose Level 2	Dose Level 1	Dose Level -1	Dose Level -2	Dose Level -2 schedule but 100mg daily

mg = milligrams; po = orally; BID = twice daily

**Patients requiring a dose reduction to below 100 mg daily of vorinostat at dose level -2 schedule will discontinue vorinostat permanently.

Table 7. Vorinostat Dose Delay Guidelines

Grade of Event	Management/Next Dose for Vorinostat
≤ Grade 1	No change in dose.

Grade 2	If tolerable to patient, no change needed but monitor patient more frequently. If intolerable to patient, hold* drug until toxicity \leq Grade 1 then resume drug at same dose.
Grade 3 (1 st occurrence)	Hold* until \leq Grade 1. Resume at same dose.
Grade 3 (after 1 st dose reduction)	Hold* until \leq Grade 1: if toxicity related to drug, resume at 1 dose lower; if toxicity not related to drug, resume at same dose or 1 dose lower.**
Grade 3 (subsequent occurrences)	Hold* until \leq Grade 1: if toxicity related to drug, resume at 1 dose lower; if toxicity not related to drug, resume at same dose or 1 dose lower**.
Grade 4	Discontinue vorinostat. However, if patient is clearly benefiting from treatment, may continue after recovery to \leq Grade 1 at PI's discretion.

*If optimally managed, patients requiring a delay of >2 consecutive weeks will discontinue vorinostat

**Patients requiring a dose reduction to below 100 mg daily of vorinostat at dose level -2 schedule will discontinue vorinostat permanently.

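### Table 4's rule for moving higher-dose patients down conflicts with the ban on dose reductions in the 42-day DLT period

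*Combined protocol and SAP*

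**What the plan says.** **Opening the next level.** Section 7.1.2 and Table 4 allow escalation once three patients at a level are evaluable with no DLT. Other patients at that level may still be at risk, that is, on treatment, without a DLT and not yet through the observation period. Section 7.2 sets that period at 42 days.

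**Moving patients down.** The double-asterisk footnote, attached to the Table 4 row for two DLTs, says: "Patients treated on a higher dose will have their treatment modified to the dose below the dose level with 2 DLTs". It applies if pending patients have DLTs. It is worded as mandatory and has no time limit.

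**Banning reductions.** Section 7.7.1 says "Vorinostat dose reductions are NOT permitted during the DLT period". It continues: "Following the completion of the DLT period, the vorinostat doses may be modified for toxicity according to the below guidelines in Tables 6 and 7". Section 7.6.1.2 says "During the Phase I portion of the study, no intrapatient dose de-escalation will be allowed during the DLT period". None of these sentences refers to the Table 4 footnote.

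**Reduction steps.** In Table 6 the first vorinostat reduction for a patient who started at Level 2 is to Level 1.

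**Evaluability.** Section 7.4 replaces escalation patients who missed 30% or more of their vorinostat doses for reasons other than DLT, who did not receive pembrolizumab, or who stopped study drug for a reason other than DLT. It does not mention patients moved under the footnote.

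**Pembrolizumab.** Section 7.6.1.2 says "After the DLT period, the following dose modifications are permitted for pembrolizumab-related adverse events". Its next paragraph says, according to irAE severity and with no time limit, to "withhold or permanently discontinue pembrolizumab and administer corticosteroids".

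**The concern.** A site with patients on Level 2 when Level 1 reaches two DLTs receives two opposite instructions. One moves those patients off a level that lies above a level just found too toxic. The other holds their dose until day 42. Nothing says which takes precedence.

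The counting is also open. A patient moved down mid-window who has no DLT could be tabulated as a DLT-free observation at full Level 2 dose, although part of the window was spent at a lower dose.

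**Working it through.** The plan states no figure on this point, so there is none to reproduce. The check has five steps.

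**1. Is the move a vorinostat reduction?** Yes. In Table 3 pembrolizumab is 200 mg at every level. If Level 1 has two DLTs, the level below it is Level -1. Planned vorinostat per 21-day cycle is:
- Level 2: 10 days × 2 doses = 20 doses; 20 × 200 mg = 4,000 mg.
- Level -1: 9 days × 2 doses = 18 doses; 18 × 100 mg = 1,800 mg.

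That is 10% fewer doses (18/20) and 55% less drug (1,800/4,000 = 0.45). Section 7.7.1 alone is therefore enough for the conflict.

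**2. Do the rules collide in time?** Let a pending Level 1 patient start on day t1 and a Level 2 patient on day t2. On the ordinary route the pending patient started first, so t1 ≤ t2. Any DLT in the pending patient falls by t1 + 42, hence by t2 + 42. The second Level 1 DLT is therefore always inside the Level 2 patient's own DLT window.

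There are two exceptions:
- A further Level 1 patient accrued under Table 4's plus-sign footnote may start after a Level 2 patient, and the inequality then need not hold.
- If Level 2 has closed and Level 1 is refilled to six and then reaches two DLTs, earlier Level 2 patients may be past day 42. The footnote then applies without conflict.

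**3. How many patients are pending?** Table 4 holds accrual at two evaluable and five in total, so three are at risk. When one of them clears, three are evaluable and two are pending. A third pending patient requires the plus-sign option.

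**4. How likely is the path?** The documents give no DLT rate, so the true Level 1 rate p is an assumption.
- Two pending, both with a DLT: (1 − p)³ × p².
- Three pending, at least two with a DLT: (1 − p)³ × [3p²(1 − p) + p³].

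| Assumed p | (1 − p)³ | Two pending | Three pending |
|---|---|---|---|
| 0.20 | 0.512 | 0.512 × 0.040 = 2.0% | 0.512 × 0.104 = 5.3% |
| 0.30 | 0.343 | 0.343 × 0.090 = 3.1% | 0.343 × 0.216 = 7.4% |
| 0.40 | 0.216 | 0.216 × 0.160 = 3.5% | 0.216 × 0.352 = 7.6% |

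These figures do not allow for the chance that no Level 2 patient has yet started, so they overstate how often the conflict would bite.

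**5. Does Section 7.4 catch a moved patient?** No. Doses changed by protocol are not missed, and even the shortfall in dose count (10%) is below the 30% threshold. The patient has not stopped study drug either.

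**Pembrolizumab.** Table 5 withholds for Grade 2 pneumonitis, while the pneumonitis criterion in Section 7.2 starts at Grade 3. For such an event at cycle 2 day 1, the sentence that permits Table 5 changes only after the DLT period and the severity-based instruction that follows it point different ways. Section 7.7.1 expressly allows vorinostat delays in the DLT period; Section 7.6.1.2 has no matching sentence for pembrolizumab.

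**The case against.** **The bans may cover only a patient's own toxicity.** The ban in Section 7.6.1.2 stands under the pembrolizumab heading. Section 7.7.1 introduces Tables 6 and 7 as changes for toxicity, whereas the footnote is a cohort action triggered by other patients' DLTs. This is a reasonable guess at the intent, and it means that Table 6 does not strictly contradict the footnote. But neither ban states that limit. Table 6 also leads from Level 2 to Level 1, here the level with two DLTs, so its relation to the footnote needs stating.

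**The footnote does not say where the pending patients are.** That they are at the lower level is inferred from the logic of the table. It is the natural reading.

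**Dose finding appears to be complete.** Section 4.6.4 reports 42 patients enrolled and adds ten to the expansion cohort, which Section 7.5 opens only after the RP2D is set. Four levels of at most six evaluable patients make 24. This stands: new wording would probably protect no future escalation patient. What remains is the accuracy of the text and of the final DLT table.

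**Withholding pembrolizumab is not de-escalation.** This also stands, and Section 7.4 already deals with a missed pembrolizumab dose or a stopped drug. A reader might infer a second gap in DLT evaluability; the documents do not support that. Only the two statements on timing need reconciling.

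**Conclusion.** The conflict is real on the ordinary escalation route. It rests on the text and on the order in which patients start, not on any assumed rate. It does not arise every time the footnote applies, because the footnote can also operate after day 42.

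The path is uncommon: about 2% to 3.5% with two pending patients at assumed DLT rates of 20% to 40%. The 5.3% to 7.6% range applies only if a third Level 1 patient is accrued under the optional footnote.

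A reader might infer that counting moved patients as DLT-free at Level 2 would bias the MTD or RP2D. The documents do not support this. Once Level 1 has two DLTs, Section 7.1.2 ends escalation and Table 4 sends accrual to a lower level. On the ordinary route Level 2 then holds at most three patients, all within their first 42 days. Sections 7.1.2 and 7.3 require six treated patients for an MTD. The harm is therefore contradictory instructions for individual patients and a possibly wrong Level 2 DLT table. No sample-size figure changes.

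**What to change.** 1. Reconcile the Table 4 footnote with Sections 7.6.1.2 and 7.7.1 and with Table 6, so that one rule governs a higher-level patient inside the DLT window. Which clinical rule applies is for the investigator.
2. Reconcile the two statements in Section 7.6.1.2 on when pembrolizumab may be changed for irAEs, again leaving the clinical choice to the investigator.
3. Add a counting rule to Section 7.4. A patient whose dose is changed under the footnote before day 42 without a DLT is not DLT-evaluable at the assigned level. A patient who already had a DLT is counted there. No replacement is accrued to a level that Table 4 has closed.
4. Check from the dose-escalation records whether the footnote was ever used, and apply the counting rule in the final DLT tabulation.

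The cost is protocol wording, one counting rule and one look at existing records. No patients are added. If the footnote was used, the Level 2 DLT denominator falls by the number of patients moved without a DLT.

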7.2 Definition of Dose-Limiting Toxicity

The dose-limiting toxicity (DLT) observation period will be 42 days (2 cycles). DLT assessment will occur on cycle 3, day 1 prior to receipt of cycle 3, day 1 of study therapy. Toxicities will be graded according to the National Cancer Institute Common Terminology Criteria for Adverse Events (CTCAE, Version 4.03) accessible at:

http://evs.nci.nih.gov/ftp1/CTCAE/CTCAE_4.03_2010-06-14_QuickReference_5x7.pdf

DLT will be defined as one of the following AEs that is at least possibly related to study treatment.

Hematologic

- Grade 4 neutropenia lasting > 7 days (despite the use of growth factor support).
- Grade 4 thrombocytopenia lasting > 7 days or requiring platelet transfusion.
- Grade 3 or 4 thrombocytopenia associated with grade 2 or higher bleeding.
- Grade 4 anemia not associated with lymphoma.

- Any Grade 5 AE.

Non-hematologic

- Grade ≥ 3 pneumonitis that does not resolve to grade ≤ 1 within 3 days after initiation of supportive care measures.
- Any clinically relevant grade 3 or grade 4 AE with the exception of:
 - Grade 3 asymptomatic laboratory abnormalities, including lipase or amylase, that are not clinically relevant, not requiring hospitalization or delay of treatment.
 - Grade 4 laboratory abnormalities including, but not limited to, hypo- or hyperglycemia, hypo- or hypernatremia, hypo- or hyperkalemia, hypo- or hypermagnesemia, hypo- or hyperphosphatemia, or hyperuricemia that resolve within 48 hours to Grade ≤ 2 with supportive measures.
 - Grade 3 nausea, or fatigue controlled with supportive measures.
 - Grade 3 vomiting if the subject does not require total parenteral nutrition (TPN), tube feeding, or hospitalization, and the toxicity improves to $<$ grade 3 within 72 hours.
 - Grade 3 asymptomatic endocrinopathy.
 - Grade 3 fatigue related to endocrinopathy that resolves within 7 days of hormone-replacement or corticosteroid therapy.
 - Grade 3 local inflammatory response attributed to local antitumor response.
 - Vitiligo or alopecia of any grade.
- Any Grade 5 AE.

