10.2 Endpoint Definitions

Overall Response Rate (ORR): Defined as the proportion of patients that have a documented CR or PR at any time during study treatment.

Complete Response (CR) rate: Defined as the proportion of patients that have a documented CR at any time during study treatment.

Duration of Response (DOR): Defined as the time from the first achievement of PR or CR to time of PD. Patients who never achieve PR or CR are excluded. Patient who has not had disease progression/relapse at last follow-up is censored at the time of last follow-up. If a patient receives non-protocol anti-lymphoma treatment prior to disease progression, the patient is censored at the time of non-protocol anti-lymphoma treatment.

Overall Survival: Defined as time from initiation of study therapy to death from any cause. If a patient is alive at the last evaluation time period, survival time is censored at the time of last follow-up.

Progression-Free Survival (PFS): Defined as the time from initiation of study therapy to the first observation of disease relapse/progression or death from any cause, whichever occurs first. If the patient has not progressed relapsed or died, the patient is censored at the time of last follow-up. If a patient receives non-protocol anti-lymphoma treatment prior to disease progression, the patient is censored at the time of non-protocol anti-lymphoma treatment.

Toxicity: Toxicity and adverse events will be recorded using the NCI CTCAE 4.03 scale. Observed toxicities will be summarized by type (organ affected or laboratory determination such as absolute neutrophil count), severity (by NCI CTCAE v4.03 and nadir or maximum values for lab measures), date of onset, duration, reversibility, and attribution.

Unacceptable Toxicity: defined as one of the following AEs that is at least possibly related to study treatment, at any point on study therapy:

- Any Gr 3 or higher IrAE that does not resolve to Gr ≤ 1 within 7 days with the exception of:
 - Grade 3 immune-related hepatitis if ALT or AST $< 8 \times$ ULN or total bilirubin $< 5 \times$ ULN.
 - Grade 3 asymptomatic endocrinopathy.
 - Local inflammatory response to study therapy.
- Any other Gr ≥ 4 AE with the exception of:
 - Non-clinically significant laboratory abnormalities
 - Local inflammatory response to study therapy.
- Any Gr 5 AE.

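### Section 7.2 can drop a promptly corrected Grade 4 laboratory abnormality from the DLT count while counting the same abnormality at Grade 3

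*Combined protocol and SAP*

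**What the plan says.** The non-hematologic part of Section 7.2 opens with the parent line "Any clinically relevant grade 3 or grade 4 AE with the exception of", followed by a list of exceptions. Two of them concern laboratory values.

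- Grade 3: "Grade 3 asymptomatic laboratory abnormalities, including lipase or amylase, that are not clinically relevant, not requiring hospitalization or delay of treatment". There is no time limit.
- Grade 4: "Grade 4 laboratory abnormalities including, but not limited to, hypo- or hyperglycemia", continuing through other analytes to "or hyperuricemia that resolve within 48 hours". The event must fall to Grade 2 or lower with supportive measures. Symptoms, clinical relevance, hospitalization and treatment delay are not mentioned.

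Five other sections bear on what happens to such an event:

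- Section 7.1.2 declares the MTD at the highest level with six patients treated and at most one DLT. Section 7.3 puts the limit at under 33% of evaluable subjects.
- Section 7.4 replaces a patient who stops study drug during the DLT period for a reason other than DLT.
- Section 7.7.1 makes missing more than 30% of vorinostat doses because of toxicity a DLT.
- Section 7.12 lists both DLT and Section 10.2 unacceptable toxicity as reasons for discontinuation.
- Section 10.2 counts any other at least possibly related event of Grade 4 or higher as unacceptable toxicity. Its laboratory exception is "Non-clinically significant laboratory abnormalities", and it gives no 48-hour allowance.

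**The concern.** A DLT definition should not count the milder form of an event and drop the more severe form under otherwise identical circumstances. Here a clinically relevant Grade 3 electrolyte abnormality that is corrected in a day counts. The same abnormality at Grade 4, with symptoms and a hospital admission, does not count if it is down to Grade 2 by 48 hours.

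The Grade 3 exception is also circular. It exempts abnormalities that are not clinically relevant, but the parent line has already removed those. Read literally, it exempts nothing.

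The DLT count fixes the MTD and, through it, the RP2D given to the 40-patient expansion cohort. An uncounted event makes a level look safer than it was.

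**Working it through.** **1. The plan's own cut-off.** 1/6 = 16.7%, which is below 33%. 2/6 = 33.3%, which is not. The largest passing count in six is therefore 1, and Sections 7.1.2 and 7.3 agree. One reclassified patient can move a level from 2/6 (fails) to 1/6 (passes).

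**2. The two laboratory exceptions side by side.** Take a clinically relevant, at least possibly related laboratory abnormality and vary three yes/no features: symptoms, hospitalization or delay, and fall to Grade 2 or lower within 48 hours. That gives 2 × 2 × 2 = 8 combinations.

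| | Fell to Grade ≤ 2 within 48 h (4 combinations) | Did not (4 combinations) |
|---|---|---|
| Grade 3 (if the rule is applied at that grade) | DLT in 4 | DLT in 4 |
| Grade 4 | exempt in 4 | DLT in 4 |

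For Grade 3, the 48-hour column is read as prompt correction of the abnormality. Grade 3 is a DLT in 8 of 8 combinations and Grade 4 in 4 of 8. The four exempt Grade 4 combinations include the symptomatic, hospitalized one. In no clinically relevant combination is Grade 3 exempt and Grade 4 counted.

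**3. When the missed-dose rule catches the event.** At levels 1 and 2, Table 3 gives vorinostat twice daily on 10 days per 21-day cycle. Two cycles hold 2 × 10 × 2 = 40 doses. If no earlier dose was missed and vorinostat stops for toxicity after *n* dosing days of cycle 2, the missed fraction is 2 × (10 − *n*)/40.

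- Stop after cycle 2 day 3 (day 21 + 3 = 24): 14/40 = 35%, above 30%, so a DLT under Section 7.7.1.
- Stop after cycle 2 day 4 (day 25): 12/40 = 30%, not above 30%, so not a DLT under that rule.

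Three outcomes follow for a clinically significant Grade 4 laboratory event corrected within 48 hours:

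- Vorinostat stops for toxicity by about day 24: the patient is counted through Section 7.7.1.
- Treatment stops later in the 42 days, as Section 7.12 read with Section 10.2 would have it: no DLT, and Section 7.4 replaces the patient. The patient leaves both numerator and denominator.
- Treatment continues without enough missed doses: the patient stays evaluable, with no DLT.

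**4. Size, as an illustration.** The documents give no event rates. Assume counted DLTs occur in 20% of patients and a further *q* have only an exempt event. The chance that a level of six passes is

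P(X ≤ 1) = (1 − p)^6 + 6p(1 − p)^5.

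| Events counted | p | P(at most 1 of 6) |
|---|---|---|
| Exempt events left out | 0.20 | 0.262 + 0.393 = 0.655 |
| Counted, q = 2% | 0.22 | 0.606 |
| Counted, q = 5% | 0.25 | 0.534 |
| Counted, q = 10% | 0.30 | 0.420 |

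This keeps the exempt patient among the six. Where Section 7.4 replaces the patient, the replacement brings a fresh DLT risk, so the figures do not describe that route exactly.

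**The case against.** The strongest reply has four parts.

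- **The conditions differ in kind.** Grade 4 carries a 48-hour limit that Grade 3 lacks. This stands as a limit on scope. A reader might infer that Grade 4 is always treated more leniently. It is not, since a clinically relevant Grade 4 abnormality that has not fallen to Grade 2 by 48 hours still counts. A separately recorded, clinically relevant Grade 3 or 4 event arising from the abnormality also remains under the parent line.
- **Sections 7.2 and 10.2 need not coincide.** Section 7.1.1 allows for unacceptable toxicity other than DLT, and Section 10.2 applies throughout therapy. This also stands, so the mismatch alone is not the defect. The problem is its combination with replacement under Section 7.4.
- **There are backstops.** The missed-dose rule catches earlier stops for toxicity. Section 7.3 lets the principal investigator choose an RP2D below the MTD. The Section 11.2 stopping rule counts unacceptable toxicity, but only at the RP2D. None of these restores a promptly corrected Grade 4 event to the DLT count when vorinostat continues or stops late.
- **Escalation is over.** Section 4.6.4 reports 42 patients already enrolled and adds 10 to the expansion. Four levels of six allow at most 24 evaluable escalation patients, and 12 were expected. New wording would probably not steer any dose decision, so the useful remedy is retrospective.

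A reader might also infer that the two fatigue exceptions, "Grade 3 nausea, or fatigue controlled with supportive measures" and "Grade 3 fatigue related to endocrinopathy that resolves within 7 days of hormone-replacement or corticosteroid therapy", contradict each other. The text does not support this. They are separate items in one list, and meeting either is enough. They overlap, and both concern Grade 3 only, so neither lets a higher grade out of the count.

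**Conclusion.** The inconsistency is in the current text and is confined to non-hematologic laboratory abnormalities. It is unequivocal for clinically relevant events that are corrected within 48 hours: always a DLT at Grade 3, never under the laboratory exceptions at Grade 4. Loss from the denominator as well is narrower. At levels 1 and 2 it needs treatment to stop after about day 24, given no earlier missed doses.

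One such patient is enough to change a level's result. The illustrated gap in pass probability is about 5 to 24 percentage points (65.5 − 60.6 and 65.5 − 42.0). It rests on the assumed 20% and 2-10% rates and on exempt events falling in patients with no other DLT.

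A reader might infer that the MTD was set too high. The documents do not show that. They report no DLT data, and no such event may have occurred.

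**What to change.** - Reconcile the Grade 3 and Grade 4 laboratory exceptions in Section 7.2 with each other and with the parent line. Make the result consistent with Sections 7.4, 7.7.1, 7.12 and 10.2. In particular, state how a patient stopped during the DLT period for a Section 10.2 event that is not a DLT enters the count. The clinical threshold is for the sponsor to set.
- Re-read the recorded cycle 1-2 events. Section 9.2.2 requires all grades with start and stop dates for those cycles. Dates alone may not settle the 48-hour condition, so the source laboratory results may be needed.
- Report the DLT count and evaluable denominator for each dose level twice, with the promptly resolved Grade 4 laboratory events excluded and then included. Identify any patient replaced after such an event.

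The cost is a wording amendment and a small re-analysis of existing data. A level's DLT count may come out less favourable.
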